10.4.6 Other Safety Analyses

Dosing information will be summarized overall subjects and listed for each subject will be listed. Discontinuation of treatment will be summarized by treatment received. The primary reason for trial drug discontinuation will also be summarized by treatment received.

Adverse events (AEs) will be coded using the MedDRA dictionary. An AE is treatment emergent if it occurs or worsens after the first dose of study treatment.

Frequencies and percentages of subjects with treatment-emergent adverse events (TEAEs), serious TEAEs, and TEAEs causing premature treatment discontinuation will be provided by treatment group. Furthermore, frequencies will be given of subjects with TEAEs by system organ class and preferred term for the following categories of AEs:

- All TEAEs
- TEAEs at least possibly related to study treatment
- TEAEs leading to study treatment discontinuation
- Serious TEAEs
- By maximal severity
- By study day of onset

Separate analyses will be performed for ocular and non-ocular AEs. Separate analyses of AEs will be generated for the Safety population with 6 weeks of follow-up and the Safety-LTFU population with 6 months of follow-up (or 1 year of follow-up).

Other safety endpoints will be summarized by treatment group and visit using descriptive statistics. Changes or shifts from baseline will also be summarized where appropriate. Separate analyses will be generated for the Safety population with 6 weeks of follow-up and the Safety-LTFU population with 6 months of follow-up (or 1 year of follow-up).

Assessments performed by eye will be summarized separately for right eye and left eye.

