	
• Visit 1 = Screening & Randomization• Visit 2 = Day 29 ± 3, 4-Week Follow-Up• Visit 3 = Day 43 ± 4, 6-Week Follow-Up (Exit for approximately 300 subjects)• Visit 4 = Day 90 ± 7, 3-Month follow-up• Visit 5 = Day 180 ± 7, 6-Month follow-up• Visit 6 = Day 270 ± 10, 9-Month follow-up• Visit 7 = Day 360 ± 10, 1-Year follow-up & Exit
Measures Taken to Reduce Bias:	Randomized treatment assignment, double-masked trial
Study Population Characteristics	
Number of Subjects:	Approximately 1050 subjects are expected to be screened to enroll 850 subjects into the trial. Approximately 550 subjects will continue after Week 6 for the Long-Term Follow-up portion, with the goal of approximately at least 100 reproxalap subjects completing at 1 year.
Condition/Disease:	Dry Eye Disease (DED)

Inclusion Criteria:	Subjects must meet all of the following criteria: 
1. At least 18 years of age (either gender and any race);2. Ability to provide written informed consent and sign the Health Information Portability and Accountability Act (HIPAA) form;3. Reported history of dry eye for at least 6 months prior to Visit 1;4. History of use or desire to use eye drops for dry eye symptoms within 6 months of Visit 1; 
Exclusion Criteria:	Subjects must not meet any of the following criteria: 
1. Clinically significant slit lamp findings at Visit 1 that may include active blepharitis, meibomian gland dysfunction (MGD), lid margin inflammation, or active ocular allergies that require therapeutic treatment, and/or in the opinion of the investigator may interfere with study parameters;2. Diagnosis of an ongoing ocular infection (bacterial, viral, or fungal), or active ocular inflammation at Visit 1;3. Contact lens use within 7 days of Visit 1 or anticipate using contact lenses during the trial;4. Eye drop use within 2 hours of Visit 1;

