5 STUDY POPULATION

5.1 Number of Subjects (approximate)

It is estimated that approximately 1050 subjects will be screened to enroll approximately 850 subjects in a 2:1 ratio of reproxalap to vehicle. Approximately 550 subjects will continue after Week 6 for long-term follow-up, with the goal of at least 100 reproxalap subjects completing the long-term follow-up.

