10 STATISTICAL HYPOTHESES AND METHODS OF ANALYSES

10.1 Analysis Populations

Safety Population – The safety population will include all subjects receiving treatment from whom at least one safety measurement is obtained following the first dose of study drug. The safety population will be analyzed for all safety assessments.

Safety-LTFU Population – The Safety population will include all LTFU subjects receiving treatment from whom at least one safety measurement is obtained following the first dose of study drug. The Safety-LTFU population will be analyzed for all safety assessments. Subjects in the Safety-LTFU population will be analyzed as treated. Subjects in the Safety population will be analyzed as treated.

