- Proportion of subjects that experience at least one TE-SAE of the retina detected via fundoscopy categorized as probably or definitely related to IP

within 6 months/1 year of study drug dosing in the Safety-LTFU population

- Intercurrent event:
 - Discontinuation of study medications is ignored, measures obtained after discontinuation of study medication will be analyzed. [treatment policy strategy]
 - Non-optimal compliance is ignored, measures will be analyzed regardless of treatment compliance. [treatment policy strategy]
 - Use of prohibited alternative therapies is ignored, measures obtained after initiation of prohibited therapies will be analyzed. [treatment policy strategy]
 - Discontinuation of study, subjects that discontinue study prior to time point of interest for an endpoint (Ex. 6 weeks or 6 months/1 year) AND do not experience event of interest will not be analyzed. [principal stratum strategy]
 - Discontinuation of study, values post-discontinuation will not be imputed. [while on treatment strategy]
- Population-level summaries:
 - Difference in the proportion of subjects that experience at least one TE- SAE of a visual acuity decrease (defined as an increase of 0.22 or greater in logMAR score) categorized as probably or definitely related to IP
 - Difference in the proportion of subjects that experience at least one TE- SAE of an IOP increase from baseline of ≥ 10 mm Hg AND report an IOP of > 25 mm Hg categorized as probably or definitely related to IP
 - Difference in the proportion of subjects that experience at least one TE- SAE of the cornea detected via slit-lamp biomicroscopy categorized as probably or definitely related to IP
 - Difference in the proportion of subjects with at least one TE-SAE of the retina detected via fundoscopy categorized as probably or definitely related to IP

Sensitivity analyses of the primary safety endpoints may include repeating primary analyses with alternative handling of intercurrent events with different estimands. In addition, sensitivity analyses using incidence rates (events/person-time) will be produced. Details will be outlined in the SAP.

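### Section 10.4.6 gives 6-month and 1-year adverse events only as crude percentages of all treated LTFU subjects, with no visible adjustment for length of follow-up

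*Combined protocol and SAP*

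**What the plan says.** Section 10.4.6 (Other Safety Analyses) sets the summary measure for adverse events: "Frequencies and percentages of subjects with treatment-emergent adverse events (TEAEs), serious TEAEs, and TEAEs causing premature treatment discontinuation will be provided by treatment group". The breakdown by system organ class and preferred term uses counts of subjects in the same way, covering all TEAEs, those at least possibly related, those leading to discontinuation and serious TEAEs. It is done separately for ocular and non-ocular events. On time horizon: "Separate analyses of AEs will be generated for the Safety population with 6 weeks of follow-up and the Safety-LTFU population with 6 months of follow-up", with 1 year given as the alternative.

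Section 10.1 defines the Safety-LTFU denominator: "The Safety population will include all LTFU subjects receiving treatment from whom at least one safety measurement is obtained following the first dose of study" … There is no minimum follow-up. Section 10.4.3 restricts all safety analyses to observed data.

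Follow-up time enters the visible analysis text in one place, the paragraph of section 10.4.5 on sensitivity analyses of the primary endpoints (repeated in the synopsis): "In addition, sensitivity analyses using incidence rates (events/person-time) will be produced". Person-time is not defined there, and the details are left to the SAP.

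On size and retention, section 5.1 says "approximately 1050 subjects will be screened to enroll approximately 850 subjects in a 2:1 ratio of reproxalap to vehicle" and "Approximately 550 subjects will continue after Week 6 for long-term follow-up, with the goal of at least 100 reproxalap subjects completing the long-term follow-up". No completion goal is given for vehicle. The sample-size text and its two tables are not shown, so any dropout assumption there cannot be seen.

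**The concern.** In a crude percentage, a subject who leaves event-free at Week 8 counts the same as one observed event-free for a year. At 6 weeks this hardly matters. At 6 months or 1 year the percentage mixes the risk of an event with the chance of being there to report it. It then falls below the 1-year risk, and it falls further in the arm with shorter follow-up.

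The long-term tables hold what is new in this trial. The synopsis states that earlier dosing ran to at most 12 weeks. Events after that point are the ones this trial can first show, and they are also the ones that early departure removes from a crude count. The sponsor already plans person-time rates for the primary endpoints, but the visible text does not extend any such measure to the TEAE tables.

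**Working it through.** **1. Sizes from the plan.** Enrolled 850, continuing 550: 850 − 550 = 300, which agrees with the synopsis visit schedule, "6-Week Follow-Up (Exit for approximately 300 subjects". Randomisation is 2:1 and stratified by follow-up schedule (section 8.1.5), so 2:1 should hold within LTFU: 550 × 2/3 ≈ 367 reproxalap and 550 × 1/3 ≈ 183 vehicle. The completion goal is 100/367 = 27%, so it is still met with up to about 73% of that arm lost.

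**2. What a crude percentage shows.** Event risks and retention below are assumptions; the documents give neither. Take a constant hazard *h* of first event and an independent constant dropout hazard *d* over 1 year:

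- *h* = −ln(1 − true risk) and *d* = −ln(retention)
- expected crude proportion = *h*/(*h*+*d*) × [1 − (1 − true risk) × retention]

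| True 1-year risk | Retention | *h* | *d* | Calculation | Crude |
|---|---|---|---|---|---|
| 20% | 50% | 0.223 | 0.693 | 0.2435 × 0.600 | 14.6% |
| 20% | 70% | 0.223 | 0.357 | 0.3849 × 0.440 | 16.9% |
| 25% | 50% | 0.288 | 0.693 | 0.2933 × 0.625 | 18.3% |
| 20% | 27% | 0.223 | 1.309 | 0.1456 × 0.784 | 11.4% |

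With equal true risk of 20% and retention of 50% v 70%, the arm losing more looks 16.9 − 14.6 = 2.3 points safer. With true risks of 25% v 20% and the same retention, a 5-point excess shows as 18.3 − 16.9 = 1.4 points.

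**3. Range.** At a true 30% in both arms, 1-year crude percentages are 25.5% v 27.1% (retention 70% v 80%), 22.1% v 27.1% (50% v 80%) and 17.4% v 27.1% (27% v 80%). With equal retention there is no false difference: at true 20% and 50% retention, both arms show 14.6%, understated alike.

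**4. Events early instead of spread out.** Keep 20% risk and 50% v 70% retention, but put all events in the first 6 weeks (6/52 = 0.115 year, hazard 0.223/0.115 ≈ 1.93 there and zero later). Crude percentages are then 19.2% v 19.6%, so the bias nearly disappears.

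**5. How the possible remedies behave.**

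- *Constant hazard.* Expected subject-years to first event or dropout are 0.600/0.916 = 0.655 (50% retention) and 0.440/0.580 = 0.759 (70%). Rates are 0.146/0.655 and 0.169/0.759, both 22.3 per 100 subject-years, so the false difference goes.
- *All events in 6 weeks.* Subject-years over the year are 0.588 and 0.684. Rates are 0.1925/0.588 = 32.7 and 0.1961/0.684 = 28.7 per 100, a false excess in the arm that loses more. Within the first 6 weeks, subject-years are 0.0995 and 0.1014, and both arms give about 193 per 100. Splitting at Week 6 removes the artefact.
- *Kaplan-Meier.* It recovers 20% in both arms under either pattern, provided dropout is non-informative.

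**6. Direction under the primary-endpoint rule.** Section 10.4.5 removes event-free early leavers from the denominator. With the inputs of step 2 this gives 14.6/(14.6 + 40.0) = 26.8% v 16.9/(16.9 + 56.0) = 23.2%. That is the opposite direction, so the point here does not carry over to the primary endpoints.

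**The case against.** The best reply has four parts.

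- **The false difference is conditional.** It needs retention that differs between arms and events that continue through the year. The documents forecast neither. All subjects dose more often in the first 4 weeks than later, so early clustering is plausible, and step 4 shows how little bias then remains. An event that itself causes dropout is still counted. All of this stands, and the point is worded accordingly.
- **The tables are descriptive.** No test is named for them in the visible text. Formal testing concerns the primary endpoints, where person-time rates are promised. This stands and limits the weight of the point.
- **Other planned output helps the reader.** Section 10.4.6 also lists TEAEs by study day of onset, a dosing summary, and treatment discontinuation with reasons by treatment received. Disposition is summarised, and a subject leaving early should have the Visit 7 safety evaluations. These can reveal unequal follow-up. None gives a number at risk or corrects a percentage.
- **More may be specified elsewhere.** The synopsis leaves further adverse-event analyses to the SAP and gives the SAP precedence. No SAP text is in the file reviewed, and parts of section 10 are redacted. The point therefore concerns the visible text only.

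A reader might infer that the plan expects to lose 73% of the reproxalap arm. It does not say so: "with the goal of at least 100 reproxalap subjects completing the long-term follow-up" sets a minimum, not a forecast. A reader might also infer that off-drug time would be counted as exposure in the incidence-rate analysis. Person-time is undefined, so this is unsupported. Estimand 1 ignores drug discontinuation for events, so counting events and time over the same whole period would be consistent. Time on drug would be a different estimand, not a correction.

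**Conclusion.** The point holds for the Safety-LTFU tables of TEAEs, serious TEAEs and TEAEs leading to discontinuation. As visibly specified, they understate 1-year risk whenever subjects leave early, and the contrast between arms is distorted if retention differs and events are spread over the year. The size is illustrative: about 2 points at a 20% risk with 50% v 70% retention, larger with wider gaps in retention, and close to nil if events are early or retention is equal. These figures rest on constant hazards and independent dropout, with retention values that are not in the documents.

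The documents do not support saying that reproxalap will look safer, that heavy attrition is planned, or that these tables will decide the safety conclusion because primary events will be rare; the assumed event proportions are not shown. This is a worthwhile, inexpensive improvement to the reporting and not an error in a formal test.

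**What to change.** In the SAP, for the Safety-LTFU tables of all TEAEs, TEAEs at least possibly related, serious TEAEs and TEAEs leading to discontinuation, ocular and non-ocular:

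1. Add Kaplan-Meier or cumulative incidence of first event at Day 180 and Day 360 by arm, with the difference and 95% CI. This should be the main added measure because it does not need a constant hazard.
2. Show subject-years of follow-up and retention by arm beside each crude percentage.
3. Give first-event rates per 100 subject-years as a supplement, split at Week 6, because a single rate over the year can mislead if events are early.
4. In the incidence-rate sensitivity analysis of section 10.4.5, define person-time and use the same window for counting events and time.

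The cost is SAP text and extra tables from data already collected. The crude percentages can stay. The added estimates still assume non-informative dropout, which should be stated with them.

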10.4.8 Interim Analyses

[REDACTED]

[REDACTED]

11 COMPLIANCE WITH GOOD CLINICAL PRACTICES, ETHICAL CONSIDERATIONS, AND ADMINISTRATIVE ISSUES

This study will be conducted in compliance with the protocol, Good Clinical Practices (GCPs), including the International Conference on Harmonization (ICH) Guidelines, and in general, consistent with the Declaration of Helsinki. In addition, all applicable local, state, and federal requirements relevant to the use of study drugs in the countries involved will be adhered to.

11.1 Protection of Human Subjects

11.1.1 Subject Informed Consent

Informed consent/assent must take place before any study specific procedures are initiated. Signed and dated written informed consent must be obtained from each subject prior to enrollment into the study.

All informed consent forms must be approved for use by the sponsor and receive approval/favorable opinion from an IRB prior to their use. If the consent form requires revision (e.g., due to a protocol amendment or significant new safety information), it is the investigator's responsibility to ensure that the amended informed consent is reviewed and approved by Ora prior to submission to the governing IRB and that it is read, signed and dated by all subjects subsequently enrolled in the study as well as those currently enrolled in the study.

11.1.2 Institutional Review Board (IRB) Approval

This study is to be conducted in accordance with Institutional Review Board regulations (U.S. 21 CFR Part 56.103). The investigator must obtain appropriate IRB approval before initiating the study and re-approval at least annually.

Only an IRB approved version of the informed consent form will be used.

11.2 Ethical Conduct of the Study

This study will be conducted in accordance with the ethical principles that originated with the Declaration of Helsinki.

11.3 Subject Confidentiality

All personal study subject data collected and processed for the purposes of this study should be maintained by the investigator and his/her staff with adequate precautions

as to ensure that the confidentiality of the data in accordance with local, state, and federal laws and regulations.

Monitors, auditors and other authorized representatives of [REDACTED] the sponsor, the IRB approving this study, the FDA, the DHHS, other domestic government agencies, and other foreign regulatory agencies will be granted direct access to the study subject's original medical and study records for verification of the data and/or clinical trial procedures. Access to this information will be permitted to the aforementioned individuals to the extent permitted by law.

A report of the results of this study may be published or sent to the appropriate health authorities in any country in which the study drug may ultimately be marketed, but the subject's identity will not be disclosed in these documents.

11.4 Documentation

Source documents may include a subject's medical records, hospital charts, clinic charts, the investigator's study subject files, as well as the results of diagnostic tests such as X-rays, laboratory tests, and EKGs. The investigator's copy of the eCRF serves as the investigator's record of a subject's study-related data.

11.4.1 Retention of Documentation

All study-related source documents, correspondence, patient records, consent forms, record of the distribution and use of all study drug and copies of case report forms should be maintained on file for at least two years after the last approval of a marketing application in an ICH region and until there are no pending or contemplated marketing applications in an ICH region; or until at least two years have elapsed since the formal discontinuation of clinical development of the study drug. These documents will be retained for a longer period if required by the applicable regulatory requirements or by an agreement with the sponsor. It is the responsibility of the sponsor to inform the investigator/institution as to when these documents no longer need to be retained.

If the responsible investigator retires, relocates, or for other reasons withdraws from the responsibility of keeping study records, custody must be transferred to a person who will accept the responsibility. The sponsor must be notified in writing of the name and address of the new custodian.

11.5 Labeling, Packaging, Storage, Accountability, and Return or Disposal of Study Drug

11.5.1 Labeling/Packaging

Investigational drug will be packaged and labeled into clinical kits.

For the treatment period, 14 pouches will be packaged in a 2-week clinical kit. Each patient will receive the appropriate number kits for the duration

of the trial they are assigned (3 kits for the six week and fourteen for one year). Each pouch will contain five ampules to provide a sufficient supply of randomized study drug.

11.5.2 Storage of Study Drug

The study drug must be stored in a secure area accessible only to the investigator and his/her designees. The study drug will be administered only to subjects entered into the clinical study, in accordance with the conditions specified in this protocol.

11.5.3 Accountability of Study Drug

The study drug is to only be prescribed by the principal investigator or his/her named sub investigator(s), and is to only be used in accordance with this protocol. The study drug must only be distributed to subjects properly qualified under this protocol to receive study drug. The investigator must keep an accurate accounting of the study drug by maintaining a detailed inventory. This includes the amount of study drug received by the site, amount dispensed to subjects, amount returned to the site by the subjects, and the amount returned to the Sponsor upon the completion of the study.

11.5.4 Return or Disposal of Study Drug

All study drug will be returned to the sponsor or their designee or destroyed on behalf of the Sponsor following local regulations.

11.6 Recording of Data on Source Documents and electronic Case Reports Forms (eCRFs)

The investigator is responsible for ensuring that study data is completely and accurately recorded on each subject's eCRF, source document, and all study-related material. All study data should also be attributable, legible, contemporaneous, and original. Recorded datum should only be corrected in a manner that does not obliterate, destroy, or render illegible the previous entry (e.g., by drawing a single line through the incorrect entry and writing the revision next to the corrected data). An individual who has corrected a data entry should make clear who made the correction

and when, by adding to the correction his/her initials as well as the date of the correction

11.7 Publications

Authorship and manuscript composition will reflect cooperation among all parties involved in the study. Authorship will be established before writing the manuscript.

13 APPENDICES

Appendix 1: Schedule of Visits and Measurements

6 Week Follow-Up Subjects

Visit	Visit 1	Visit 2	Visit 3
	Day 1	Day 29 ± 3	Day 43 ± 4
Procedure	Screening & Randomization	Follow-up Visit	Follow-up Visit
Informed Consent / HIPAA	X		
		X	X
	X		
		X	X
		X	X
	X	X	X
	X ¹		X ¹
	X		
	X	X	X
	X		
	X	X	X
	X		
	X	X	X
	X		
	X		
	X	X	
	X	X	
			X

Long Term Follow Up Subjects

Visit	Visit 1	Visit 2	Visit 3	Visit 4	Visit 5	Visit 6	Visit 7
	Day 1	Day 29 ± 3	Day 43 ± 4	Day 90 ± 7	Day 180 ± 7	Day 270 ± 10	Day 360 ± 10
Procedure	Screening & Randomization	Follow-up Visit					
Informed Consent / HIPAA	X						
		X	X	X	X	X	X
	X						
		X	X	X	X	X	X
		X	X	X	X	X	X
	X	X	X	X	X	X	X
							X ²
	X ¹						X ¹
	X						X
	X	X	X	X	X	X	X
	X						
	X	X	X	X	X	X	X
	X						X
	X						X
	X				X		X
	X	X	X	X	X	X	X
	X	X	X	X	X	X	X
	X						
	X						
	X						
	X	X	X	X	X	X	X
	X	X	X	X	X	X	X

[figure not shown]
[figure not shown]
[figure not shown]
[figure not shown]
[figure not shown]
[figure not shown]
[REDACTED]

[figure not shown]
[figure not shown]
